4.7.4. Safety analysis

SCD complications are defined as 'Yes' to the question 'is this a SCD Complication' in the SCD complications/AE form while the other AEs are defined as 'No' to the question 'is this a SCD Complication' in the SCD complications/AE form.

All safety analyses will be based on safety analysis set (Section 4.2). The analysis period for Pre-Oxbryta is 12 months before the first dose of Oxbryta and the analysis period for post-Oxbryta is from the first dose of Oxbryta through end of the study or the date of dose pausing or treatment discontinuation if the date of end of study date is missing.

SAEs and protocol-specified AEs will be classified according to the Medical Dictionary for Regulatory Activities (MedDRA). The frequency of SCD complications and other AEs treatment-emergent adverse events (TEAEs) and treatment emergent SAEs will be tabulated by system organ class, preferred term, severity (and total), and relationship to Oxbryta® (Voxelotor) treatment. The pregnancy outcomes and fertility will be reported as a listing. Any events (including deaths) leading to discontinuation of the study and SAEs will be listed.

A TEAE is defined as an AE that occurs during the effective duration of treatment defined as the time from the first dose of Oxbryta through end of treatment date or the end of study completion/discontinuation date (if the date of end of treatment is missing) +28 days.

On the AE case report form there is a question “Did AE start prior to first dose?”

- If the response is “Yes” or the adverse event start date is missing, and the end date is prior to the first dose of Oxbryta, then the AE is not considered a TEAE
- If the response is “No” or “Unknown”, then the AE is considered a TEAE

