Regardless of how long participants have been on Oxbryta® (Voxelotor) when they enroll in the study, participants will be followed for up to 5 years after their first dose of Oxbryta® (Voxelotor) treatment, or until they withdraw their consent to participate, or are discontinued from the study. Treatment, including interruptions and restarting treatment, will continue at the discretion of the treating physician, and there are no pre-defined treatment requirements. Participants may receive any additional medications prescribed by their treating physician or have any medical interventions that are deemed appropriate by the treating physician or study doctor. The participant or treating physician may discontinue Oxbryta® (Voxelotor) at any time. Participants who discontinue treatment with Oxbryta® (Voxelotor) earlier than 5 years will continue to be followed on study to collect clinical and health-related quality of life (HRQoL) outcomes for up to 5 years after their first dose of Oxbryta® (Voxelotor) treatment.

Participant safety and tolerability will be assessed throughout the study data collection period by the study doctor and reported to the Sponsor.

The overall study design is illustrated in [Figure 1](#).

Figure 1: Study Schema

SOC, standard of care.

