10.4.1.2. Early Discontinuation of Oxbryta® (Voxelotol)

Participants may be discontinued from Oxbryta® (Voxelotol) treatment by the study doctor or treating physician at any time and for any reason.

Participants who are discontinued or withdraw from Oxbryta® (Voxelotol) treatment will continue to be followed for up to 5 years after the first dose of Oxbryta® (Voxelotol) treatment unless they withdraw consent for study participation.

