4.6. Date Imputation

For the partial AE start dates, if month and day are missing, set to June 15. If day is missing, set to 15. If the imputed AE start date is after the AE end date, set AE start date to AE end date. If the AE start date is completely missing, no imputation will be done.

If the end of study date is missing, the last known visit date will be used. If the end of treatment date is partial (month and year is known), the last day of the month is used. If the end of treatment date is partial (only year is known) or is missing completely, the end of the study date is used.

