4.7. Statistical methodology and analyses

The following general analysis will be followed for this study, unless otherwise specified.

Unless otherwise specified, continuous/quantitative variables will be summarized using descriptive statistics which will include the number of participants with data to be summarized (n), mean, standard deviation (SD), median, first and third quartile (Q1, Q3), minimum, maximum, and the number of missing observations. Minimum and maximum will be reported with the same number of decimal places as collected in raw data, while mean, median, Q1, Q3 will be reported with one extra decimal place, and SD will be reported with two extra decimal places. Descriptive statistics for categorical/qualitative variables will be presented with number of participants and percentage (%) of participants in each category.

Percentages will not include the missing category and will be calculated over the number of participants with available (non-missing) data. A category with a zero count will be presented as “0” and a category with a 100 percentage will be displayed as “100”.

The annualized incidence rate is defined as total numbers of a given event for all participants divided by the total patient-year where the total patient-year is defined as the sum of total duration (years) as defined in the Section 4.7.1 for all participants.

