4.7.1. Index date and follow-up

The index date is defined as the inform consent date. The Post Oxbryta period is from the first dose of Oxbryta to the date of end of treatment or end of study.

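### SAP 4.6, 4.7.1 and 4.7.4 do not agree on where follow-up closes when the end-of-study date is missing, and the 4.7.4 fallback can close the safety period at a temporary dose pause

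*SAP*

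**What the plan says.** Three SAP sections bear on the end of post-treatment follow-up.

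- **SAP 4.6 (Date Imputation):** "If the end of study date is missing, the last known visit date will be used". The rule is general and is not tied to one analysis.
- **SAP 4.7.4 (Safety analysis):** the post-Oxbryta analysis period runs from first dose "through end of the study or the date of dose pausing or treatment discontinuation if the date of end of study date is missing".
- **SAP 4.7.1 (Index date and follow-up):** "The Post Oxbryta period is from the first dose of Oxbryta to the date of end of treatment or end of study". It does not say which of the two dates applies when both exist, and it does not mention a pause. It also feeds the rates: under SAP 4.7, "the total patient-year is defined as the sum of total duration (years) as defined in the Section 4.7.1 for all participants".

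The design treats neither a pause nor a stop as the end of observation. Protocol 9.1.1.1 says "Treatment, including interruptions and restarting treatment, will continue at the discretion of the treating physician", and SAP 4.1 repeats this. Under Protocol 10.4.1.2, participants who come off treatment "will continue to be followed for up to 5 years after the first dose of Oxbryta® (Voxelotol) treatment unless they withdraw consent".

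The TEAE window in SAP 4.7.4 is a separate rule. It runs from first dose through "end of treatment date or the end of study completion/discontinuation date (if the date of end of treatment is missing) +28 days".

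**The concern.** Sections 4.6 and 4.7.4 give different answers to the same question for the same people, and the SAP does not say which prevails. The version history does not settle it: version 2 added both the 4.6 end-date imputation and the 4.7.4 analysis period, and changed the 4.7.1 text as well.

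The 4.7.4 fallback also fits the design poorly.

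- A pause can be followed by a restart, yet the fallback lets it close the period.
- The fallback does not say which pause counts when there are several.
- It gives no closing date for someone with no end-of-study date who never paused or stopped. Section 4.6 covers that person.

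Two things are at stake. First, recorded events could fall outside the safety period only because an administrative date is blank. Second, event counts and patient-years could close on different dates, which distorts an annualized rate. Two programmers following the SAP could produce different results. This matters in a report that SAP 4.7.3 describes as carrying full safety data and limited efficacy data.

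**Working it through.** The plan states no figure to reproduce, because SAP 4.5 gives no formal sample size calculation and none is needed for a date rule. The check compares the rules and then illustrates them on assumed dates.

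**Step 1. Closing date when the end-of-study date is missing**

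| Place | Closing date | Closed by a pause? |
|---|---|---|
| SAP 4.6 | Last known visit | No |
| SAP 4.7.4, post-Oxbryta period | Pause or treatment discontinuation | Yes |
| SAP 4.7.1, patient-years | End of treatment or end of study, unordered | No |
| SAP 4.7.4, TEAE window | End of treatment, else end of study, plus 28 days | No |
| SAP 4.7.5, post-Oxbryta VOC count | No upper date stated | No |

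**Step 2. Order of application.** If 4.6 is applied first, anyone with a recorded visit has an end-of-study date and the 4.7.4 fallback is never reached. If 4.7.4 is applied to the raw field, the period closes at the pause or stop. The SAP does not choose between these.

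**Step 3. One participant (assumed dates).** First dose at month 0, last visit at month 24, end-of-study date missing. The 4.6 window is 24/12 = 2.0 years. The share of follow-up outside the 4.7.4 window is 1 − (pause month / 24).

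| Pause month | 4.7.4 window (years) | Share outside |
|---|---|---|
| 3 | 0.25 | 1 − 3/24 = 87.5% |
| 6 | 0.50 | 1 − 6/24 = 75% |
| 12 | 1.00 | 1 − 12/24 = 50% |
| 18 | 1.50 | 1 − 18/24 = 25% |

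**Step 4. Effect on a rate (assumed 2 events per year, evenly spread, month 6).** Expected events are 2 × 2.0 = 4 over the full window and 2 × 0.5 = 1 by month 6.

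- Both parts cut at month 6: 1/0.5 = 2 per year, which is unbiased.
- Pause then restart, with events cut at month 6 and patient-years run to month 24: 1/2.0 = 0.5 per year, which is too low.
- Permanent stop at month 6, with events counted to month 24 and patient-years closed at end of treatment: 4/0.5 = 8 per year, which is too high.

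The direction therefore depends on which pair of rules is used.

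**Step 5. Cohort range (assumed).** Take 500 participants with 2 years each, or 1,000 patient-years, and a pause at month 6, so that each affected participant has 1.5 years outside the window. If 2%, 5%, 10% or 20% have both a missing end-of-study date and a pause, the time outside is 500 × share × 1.5 = 15, 37.5, 75 or 150 patient-years. That is 1.5%, 3.75%, 7.5% or 15% of the total. These are shares of time outside one window, not shares of events missing from the report.

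**The case against.** The best defence is that 4.6 is a general imputation rule, naturally applied before any analysis. The 4.7.4 fallback is then dormant for everyone with a recorded visit, including the participant in the illustration. That is a fair reading, but the SAP does not state it. If it is the intended reading, the fallback has no use for these participants and can be removed at no cost.

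The second defence is that most outputs do not depend on this period, and it largely stands. No title in SAP Appendix A names the 4.7.4 analysis period. The TEAE tables (15.3.1 to 15.3.3) use the TEAE window. A form answer of No or Unknown on whether the event began before first dose means "then the AE is considered a TEAE", with no upper date. The death and SAE listings (15.3.5 and 15.3.7) state no cut-off. SCD complications are summarized over the treatment period under SAP 4.7.3.

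A reader might infer that SAEs and deaths after a pause will disappear from the report. The documents do not support this, because the listings and TEAE tables can retain them. A reader might also infer that safety will look better than it is, on the ground that pauses tend to follow tolerability problems. The documents give no reasons for pauses, only that they are at the physician's discretion. With an even event rate, cutting events and time together leaves the annualized rate unchanged, and Step 4 shows that a mismatch can move it either way.

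**Conclusion.** The inconsistency is established from the current text: three wordings for the end of follow-up, two of which conflict directly for a missing end-of-study date, with no precedence. Where the 4.7.4 fallback operates, it closes the safety period at a pause that may be temporary, contrary to a design that allows restarts and continues follow-up after a stop.

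The consequence is conditional. It needs the fallback to be used in place of 4.6, a participant with both a missing end-of-study date and a recorded pause or stop, and an output cut to that period. The documents give neither the number of such participants nor the timing of pauses, so the size and direction of any effect are unknown. The figures in Steps 3 to 5 rest on assumed dates, rates and shares and only show the scale that is possible. The point is worth correcting because it is a wrong rule as written and is cheap to remove, not because a loss of safety events has been shown.

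**What to change.** 1. In SAP 4.7.4, end the post-Oxbryta period at end of study, and delete the rest of the wording in "through end of the study or the date of dose pausing or treatment discontinuation if the date of end of study date is missing" that refers to pausing or discontinuation.
2. State that the 4.6 last-known-visit date replaces every missing end-of-study date before any analysis period is derived.
3. Align the post-Oxbryta period in SAP 4.7.1 with this. Say which of its two end dates applies to each rate, and require events and patient-years in that rate to close on the same date. Deleting the 4.7.4 clause alone would leave the denominators ambiguous.
4. Leave the TEAE window as its own rule. A pause does not close it now.

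Extending the 4.6 date to a later recorded event or contact is optional and not needed to resolve the conflict.

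The cost is one deleted clause in 4.7.4, a sentence on precedence and a clarification in 4.7.1. No new data are needed, and nothing changes in treatment or in the follow-up of participants.

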4.5. Sample size and power calculations

The sample size is selected based on feasibility considerations to provide an estimation of the relationship between change in Hb and significant clinical events, for example VOCs and stroke that participants experience over the 5 years of the study. The total sample size of approximately 500 participants is expected to be enrolled. There is no formal sample size calculation for this study.

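### The treatment-emergent rule in SAP 4.7.4 leaves events ongoing at first dose open to two readings and contradicts itself for some events that ended before it

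*SAP*

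**What the plan says.** SAP 4.7.4 opens with a general definition: "A TEAE is defined as an AE that occurs during the effective duration of treatment". That duration runs from first dose to the end-of-treatment date, or to the end-of-study date if the former is missing, plus 28 days. The sentence does not mention onset or worsening.

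Two bullets then use a question on the adverse event form, "Did AE start prior to first dose", which can be answered *Yes*, *No* or *Unknown*.

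- Bullet 1 (exclusion) begins "If the response is “Yes” or the adverse event start date is missing" and, after a comma, continues "and the end date is prior to the first dose of Oxbryta, then the AE is not considered a TEAE". The point turns on the join between the two parts: "the adverse event start date is missing, and the end date is prior to the first dose of Oxbryta".
- Bullet 2 (inclusion) reads "If the response is “No” or “Unknown”, then the AE is considered a TEAE". It carries no date condition.

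SAP 4.6 imputes partial onset dates to mid-month or mid-year, but for the remaining case it says "If the AE start date is completely missing, no imputation will be done". The protocol has no TEAE definition; its section 9.11.4 only describes how events are tabulated.

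**The concern.** The bullets should place every event record in exactly one class. They do not, and one of the gaps depends on how a sentence is parsed.

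The rule feeds Tables 15.3.1 (all TEAEs), 15.3.2 (treatment-related) and 15.3.3 (serious). SAP 4.7.3 scopes the abbreviated report as complete safety data with limited efficacy data, so these tables carry much of its weight. There is no comparator arm, so background disease that is misclassified would be read directly as on-drug incidence. Two competent programmers working from the same SAP could produce different tables.

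The affected records are plausible. Protocol Appendix 1 schedules safety data in the pre-treatment column, and SAP 4.7.5 itself uses sickle cell events dated before treatment start. Participants may already be on drug when they consent (Protocol 9.3.1), so first dose can precede data entry by some time, which makes missing dates and *Unknown* answers more likely.

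**Working it through.** There is no plan figure to reproduce. This is a classification rule, and SAP 4.5 states "There is no formal sample size calculation for this study". The check is a full enumeration.

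**Inputs (SAP 4.7.4).** Form answer (*Yes*, *No*, *Unknown*) × start date (known, missing) × end date (before first dose; on or after first dose, or ongoing) = 3 × 2 × 2 = 12 cells.

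**Two readings of bullet 1.**

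- As punctuated: (*Yes* or start missing) and end before first dose.
- Other reading: *Yes*, or (start missing and end before first dose).

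Bullet 2 is the same in both: *No* or *Unknown* makes a TEAE.

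| Answer | Start date | End date | Cells | As punctuated | Other reading |
|---|---|---|---|---|---|
| Yes | known or missing | before first dose | 2 | not TEAE | not TEAE |
| Yes | known or missing | on/after first dose, or ongoing | 2 | neither bullet | not TEAE |
| No or Unknown | known | before first dose | 2 | TEAE | TEAE |
| No or Unknown | missing | before first dose | 2 | both bullets | both bullets |
| No or Unknown | known or missing | on/after first dose, or ongoing | 4 | TEAE | TEAE |

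**Totals.** As punctuated: 2 not TEAE, 6 TEAE, 2 in conflict, 2 unassigned. Other reading: 4 not TEAE, 6 TEAE, 2 in conflict, 0 unassigned.

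**What follows.**

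1. The two unassigned cells are exactly the *Yes* events not over by first dose. Only the general definition is left to decide them. An event in progress during treatment can be said to occur during it, so they can be counted.
2. The two conflict cells do not depend on the reading. SAP 4.6 does not resolve them, because a completely missing start date stays missing.
3. An *Unknown* event with a known start and a pre-dose end is a TEAE by bullet 2 on both readings, although its dates show it was over before exposure. The matching *No* cell is a record that contradicts itself, and it is also counted.

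**Size.** The two readings can differ in the any-TEAE percentage by k/N. Here k is the number of participants whose only candidate event is a *Yes* event ongoing at first dose, and N is the size of the safety analysis set. The documents give nothing from which to obtain k.

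**The case against.** The other reading may well be what was intended. The form question asks about onset, and excluding every event that began before first dose is a natural rule. Even as punctuated, no bullet labels an ongoing *Yes* event as a TEAE. A reader might infer that such events will be counted; the text supports only that their status is not stated and that the general wording allows it.

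A reader might also infer that, on the other reading, a pre-existing event that becomes serious on drug disappears. It does not. SAP 4.7.4 lists serious events with no treatment-emergent restriction, and Table 15.3.7 is that listing. The event would leave the TEAE counts but still be reported.

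A third inference is that long-lasting complications such as leg ulcers would dominate the error. The documents do not establish this. Pre-treatment complications have their own form (SAP 4.3), and complications have separate Tables 15.2.5 and 15.2.6. SAP 4.7.5 does allow sickle cell events on the adverse event form before treatment start, so there is some overlap, but its extent is unknown.

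Finally, the tables are descriptive, the conflict cells are narrow, and the punctuated reading tends to over-count rather than hide events. All of this limits how strongly the point can be put. It does not remove it: the SAP does not state the intended grouping, and the conflict and *Unknown* cells are wrong on either reading.

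**Conclusion.** The TEAE bullets are ambiguous for one class of events and contradictory or unsuitable for others. As punctuated, 2 of 12 cells have no assignment and 2 have two opposite ones; on the other reading the 2 conflicts remain. On both readings, *Unknown* events with dates wholly before first dose are counted as treatment emergent.

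The effect on Tables 15.3.1 to 15.3.3 cannot be computed from the documents, and any percentage range would be invented. The finding rests only on the wording of SAP 4.6 and 4.7.4 and on the absence of a resolving rule elsewhere. It does not show that the tables will be inflated, nor that serious worsening will go unreported. Because the rule drives the main safety tables and is cheap to repair, it should be corrected before they are finalised.

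**What to change.** Define a TEAE by onset within the window the SAP already states: first dose to end of treatment, or to end of study if that date is missing, plus 28 days. Replace the two bullets with steps applied in order:

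1. An event whose end date precedes first dose is not a TEAE, whatever the form answer.
2. Otherwise a complete recorded start date decides. If it conflicts with the form answer, query the record.
3. If the start date is partial or missing, the form answer takes precedence over any imputed date. *Yes* is not a TEAE. *No* or *Unknown* is a TEAE unless the event is shown to fall outside the window.

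As the one exception, count a pre-existing event as a TEAE where the form records an increase in severity or seriousness after first dose. Otherwise leave it to the serious event listing (Table 15.3.7).

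Leaving that exception aside, all 12 cells now have one outcome (taking a known start as complete). The 6 with a pre-dose end date are excluded by step 1. The 3 others with a known start are decided by that date. Of the 3 with a missing start, *Yes* is excluded and *No* and *Unknown* are included.

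The cost is SAP wording, a derivation change and some data queries. The documents do not show that post-dose changes in severity are captured, so the exception should use only what is on the form. The small downside is that some pre-existing events that worsened without a recorded change will not be counted as TEAEs.

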1. VERSION HISTORY AND LIST OF ABBREVIATIONS

Version history

Version/ Date	Associated Protocol Amendment	Rationale	Specific Changes
2/ 21-Nov-2024	Original Protocol 10 October 2023	Update to Section headers to provide clarity for the analysis and list of tables.	
Section 3.2: Updated SCD complications.
 
Section 4.2.1: Added subgroup in this section
 
Section 4.3: Modified age was based on the first dose of Oxbryta.
 
Section 4.6: Added imputation rule for the end of study and treatment dates
 
Section 4.7.1: Modified texts about post-Oxbryta
 
Section 4.7.3: Modified SCD-related events
 
Section 4.7.4:
 
 Removed the sentence of SCD related events Added an analysis period Added SAE listings Added 28 days to the TEAEs definition 
Section 4.7.5:
 
 Modified the title to subgroup analyses Added analysis for new added subgroup 
Appendices:
 
 Removed ‘Study Drug Administration and Dosage Changes Initiated by the Participant’ table Modified title for tables 15.2.5, 15.2.6, and 15.4 Added table 15.2.5.1 ‘Summary of Transfusions’ Added table 15.2.6.1 ‘Annualized Incidence Rate of Transfusions’ Updated table 15.3.3 title Added table 15.3.7 Added tables 15.5.1-15.5.4

3/ 24-Jan-2025	Original Protocol 10 October 2023	Update to Section headers to provide clarity for the analysis and list of tables.	Section 4.2: Modified analysis populations Section 4.7.3: Added texts to exclude lab values with the incorrect unit. Appendix 6.1: Modified the analysis population in the table title
-------------------	--	--	---

List of abbreviations

Abbreviation	Definition
ACR	albumin/creatinine ratio
ACS	acute chest syndrome
AE	adverse event
ALT	alanine aminotransferase
ANC	absolute neutrophil count
AST	aspartate aminotransferase
CGIC	Clinical Global Impression of Change
CRF	case report form
CKD-EPI	Chronic Kidney Disease Epidemiology Collaboration
CSR	Clinical Study Report
ED	emergency department
EDC	electronic data capture
eGFR	estimated glomerular filtration rate
ESA	erythropoietin-stimulating agent
FDA	(US) Food and Drug Administration
Hb	hemoglobin
HbF	fetal hemoglobin
HbS	sickle hemoglobin
HRQoL	health-related quality of life
ICF	Informed consent form
ICH	International Conference on Harmonization
ICU	intensive care unit
IRB	Institutional Review Board
LDH	lactate dehydrogenase
MCV	mean corpuscular volume

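### The safety endpoint on adverse events that led to Oxbryta dose change or stopping has no planned analysis, and the TEAE rule beside it needs a wording repair

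*SAP*

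**What the plan says.** **Endpoint.** The Protocol abstract, Protocol 8.1.1.3 and SAP 3.3 each list, among three safety endpoints, the rate of adverse events that led to an Oxbryta dose change or to stopping Oxbryta.

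**Planned safety analysis.** Protocol 9.11.4 tabulates events by system organ class, preferred term, severity and relationship to drug. SAP 4.7.4 uses the same factors. Action taken with the drug is not among them. On discontinuation, SAP 4.7.4 says only: "Any events (including deaths) leading to discontinuation of the study and SAEs will be listed". Table 15.3.6 in SAP Appendix A carries this out, with a title that also refers to the study. Table 15.1.5 is an exposure table on dosage changes made by the physician.

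**Follow-up after stopping.** Protocol 10.4.1.2 and SAP 4.1 keep participants who stop Oxbryta in follow-up for up to 5 years from first dose.

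**TEAE rule.** SAP 4.7.4 ends the treatment-emergent window at "end of treatment date or the end of study completion/discontinuation date (if the date of end of treatment is missing) +28 days". The version history records this as a deliberate change: "Added 28 days to the TEAEs definition". Two bullets follow, tied to a CRF question on whether the event began before first dose. The second reads: "If the response is “No” or “Unknown”, then the AE is considered a TEAE".

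**The concern.** SAP 4.7.3 describes an abbreviated report in which efficacy is limited but safety is complete. A named tolerability endpoint with no planned output does not fit that description. Whether it appears in the report, from which forms, with what denominator and in what format would all be decided after the data are in hand.

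The listing that does exist can mislead by its closeness. Someone who stops Oxbryta because of an adverse event and stays in the registry, as the design intends, need not appear in Table 15.3.6. Someone who leaves the study because of an event does appear there.

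The TEAE point is secondary. A programmer who applied the second bullet literally would count any event after first dose, however long after the drug was stopped. The 28-day limit would then have no force in Tables 15.3.1 to 15.3.3.

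**Working it through.** No figure in the plan can be reproduced here. The check sets the passages side by side.

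**1. Output titles in SAP Appendix A.** 15.1.1–15.1.5 give 5. 15.2.1–15.2.8 with 15.2.5.1 and 15.2.6.1 give 10. 15.3.1–15.3.7 give 7. 15.4 gives 1. 15.5.1–15.5.5 give 5. Total: 5 + 10 + 7 + 1 + 5 = 28.

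- Titles naming adverse events that led to Oxbryta dose modification or stopping: 0 of 28.
- Titles naming adverse events that led to leaving the study: 1 of 28 (Table 15.3.6).

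**2. Could a neighbouring output stand in?**

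| Output | What the endpoint needs | What the output gives |
|---|---|---|
| Table 15.3.6 | Event that led to stopping the drug; a rate | Event that led to leaving the study; a listing |
| Table 15.1.5 | Dose change linked to an adverse event | Exposure table, physician-initiated changes, no stated link to events |
| Tables 15.3.1–15.3.3 | Action taken with the drug | Class, term and severity; relatedness in 15.3.2; no action taken |

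If the word study in Table 15.3.6 were a slip for study drug, it would still be a listing without a rate and would still omit dose modification. SAP 4.7.4 uses the same word in its text, so a slip in one title is not the obvious explanation.

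**3. Data sources.** SAP 4.3 retains the combined SCD complications/adverse events form, the end-of-treatment form and the physician-administration form. Protocol 9.4 also had a participant-adherence form, which SAP 4.3 no longer lists. The SAP version history records that version 2 removed the table of dosage changes made by the participant. SAP 4.7.3 nevertheless still says that changes by both participant and physician will be summarized.

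**4. TEAE definition against the CRF bullets.**

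| Case | Definition | Bullets, read literally |
|---|---|---|
| Onset within the window, answer *No* | TEAE | TEAE |
| Onset more than 28 days after end of treatment, answer *No* | Not a TEAE | TEAE |
| Start date completely missing, answer *No* or *Unknown* | Cannot be evaluated | TEAE |
| Recorded pre-dose onset, answer *Unknown* | Not a TEAE | TEAE |
| Answer *Yes*, event ended after first dose | Depends on the meaning of occurs | Depends on parsing |

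Row 2 is the open end. Such events can be in the database, because SAP 4.7.4 itself says that the "analysis period for post-Oxbryta is from the first dose of Oxbryta through end of the study".

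Row 3 shows why the bullet is needed: SAP 4.6 leaves completely missing start dates unimputed. Row 4 requires inconsistent data.

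Row 5 turns on the words "or the adverse event start date is missing, and the end date is prior to the first dose of Oxbryta". If the end-date condition governs both alternatives, a *Yes* event that ended later falls outside the bullet. If it governs only the missing-date alternative, every *Yes* event is not a TEAE.

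Partial dates add one more gap. Under SAP 4.6, "if month and day are missing, set to June 15", so an imputed start can fall on the other side of first dose from the CRF answer. The SAP does not say which prevails.

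**The case against.** **On the endpoint.** Titles are not contents. Table shells are not shown, and Table 15.1.5 or the event tables could carry reasons or action taken. The SAP follows Protocol 9.11.4, so the gap starts in the Protocol and is not a choice made in the SAP. Protocol 8.1 makes every outcome conditional on available data, and the report is descriptive and abbreviated.

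Much of this stands as a limit on the claim. It does not supply an analysis: no text in either document plans one. The SAP also shows how it handles outcomes it gives up. SAP 4.7.3 drops PROMIS in so many words and gives sparse response as the reason. There is no such sentence for this endpoint.

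**On the TEAE rule.** The window sentence comes directly before the bullets, and the CRF question asks only about onset relative to first dose. It is natural to read the bullets as settling the start of the window and leaving the end alone. Table 15.3.7 lists SAEs under a title not restricted to treatment-emergent events, so late SAEs appear reportable either way. For participants whose end-of-treatment date is missing, the SAP extends the window on purpose: "If the end of treatment date is partial (only year is known) or is missing completely, the end of the study date is used". These points stand, and they reduce this part to a matter of wording.

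**Stronger readings that the documents do not support.** A reader might infer that the TEAE tables will be inflated by off-drug events. Under the natural reading the effect is zero. Under the literal one it cannot be sized, because the documents give no stopping rate, stop times or data cut-off. A reader might also infer that *Yes* events continuing past first dose are left unclassified. That is only one of two parsings, so the bullet is ambiguous rather than silent.

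**Conclusion.** The main point holds and should be fixed before the report is written. A safety endpoint named in both documents has no planned analysis: 0 of 28 listed outputs cover it, and the only discontinuation output (1 of 28) concerns a different event and gives no rate. This rests on the text of Protocol 9.11.4 and SAP 4.7.4 and on the Appendix A titles, since shells are not shown. It does not show that the endpoint was dropped on purpose, nor that the data exist. The documents do not say whether the forms record why a dose was changed or stopped.

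The TEAE point holds only as a minor wording repair, with no effect size claimed.

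**What to change.** **Endpoint.** Add to SAP 4.7.4 and Appendix A a table on the safety analysis set of adverse events that led to Oxbryta dose modification and, separately, to Oxbryta discontinuation. Give n, % and a rate per patient-year, and state the denominator. Draw on the adverse event, end-of-treatment and physician-administration forms. Keep Table 15.3.6 as an additional listing.

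Include participant-initiated changes only if those data are still in the database. In either case, reconcile SAP 4.7.3, which promises them, with SAP 4.3 and Appendix A, which no longer provide for them. If the reason for a change or stop was not recorded, say in the SAP and the report that the endpoint cannot be estimated, as was done openly for PROMIS.

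**TEAE wording.** State in SAP 4.7.4 that:

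- the CRF question settles only the start of the window, and is used when the event start date is missing or partial;
- an event with known onset more than 28 days after end of treatment is not a TEAE;
- an event with a completely missing start date answered *No* or *Unknown* remains a TEAE;
- for a partial date, how the CRF answer and the SAP 4.6 imputed date are used together;
- which parsing of the *Yes* bullet is meant.

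**Cost.** One table and a few sentences, with no new data collection. If the reasons were not recorded, the table is replaced by a statement in the SAP and the report.
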